Protocol Number and Title: IRBNet #1629044, Promoting Benzodiazepine Cessation via Electronically Delivered Patient Self-Management Intervention

(EMPOWER for Veterans; **Aim 2**)

Funding Agency: VA Health Services Research and Development, IIR 18-026

Investigator/Study Chair: [name]

Version and Date: v6. June 7, 2023

Abstract

Background and Significance

Long-term dependency of benzodiazepine carries significant health risks among users, giving cause for alarm among populations. Although benzodiazepines can be effective in short-term use, when taken for extended periods, they create greater risks of cognitive decline and other brain damage, falls and other accidents, benzodiazepine dependence, and opioid-benzodiazepine overdose. This has become a major concern within VA, where over 350,000 Veterans are prescribed benzodiazepines annually, and two-thirds of that population takes them long-term (i.e., 3 months or more) (VA Pharmacy Benefits Management Academic Detailing Service, 2017) [5]. However, these risks might be reduced with low-cost patient self-management interventions. A paper-and-pencil version of one such intervention (Eliminating Medications Through Patient Ownership of End Results; EMPOWER) proved effective in a Canadian clinical trial with older adults (Tannenbaum et al., 2014) [15]. Ideally, digitizing such an intervention for electronic delivery and tailoring it to different populations to include Veterans could expand its reach. Accordingly, this protocol describes Aim 2 of three aims of this research study. Aim 2 specifically addresses research for a randomized controlled trial to test the effectiveness of an electronically delivered direct-to-patient intervention for promoting benzodiazepine cessation tailored to U.S. military veterans.

Specific Aims

Aim 1 has been completed. A promising non-VA benzodiazepine cessation intervention (EMPOWER) has been converted from paper & pencil to an electronic format tailored to Veterans. Aim 2, conduct a **randomized clinical trial of the effectiveness of the tailored, electronic intervention (EMPOWER for Veterans) on VA primary care patients' benzodiazepine cessation/reduction and functional outcomes is being implemented**. A third aim will seek to conduct a budget impact analysis to estimate the costs of implementing EMPOWER for Veterans throughout VA. The Palo Alto, CA site will conduct Aim 3 and thus seek approval for related study activities at their site. **This protocol seeks approval for Aim 2 of this research study.**

Innovation

Converting the effective use of the paper-and-pencil version of EMPOWER to an electronic version that works on smart phones, tablets, and/or desktop computers, the proposed project intends to tailor the electronic version (EMPOWER for Veterans) to the needs and preferences of the Veteran population; in effect reducing risks among this population of benzodiazepine users.

Methodology

When EMPOWER for Veterans is fully designed, its effectiveness will be evaluated in a two-arm individually randomized controlled trial with 170 Veterans at the Central Arkansas Veterans Healthcare system and the Minneapolis VA Health Care System, and affiliated sites. Veterans who have been taking benzodiazepines for at least 3 months and have access to a smartphone or desktop/laptop computer will be invited to participate. The primary hypothesis of the study is that Veterans receiving EMPOWER for Veterans will be significantly more likely to cease benzodiazepine use entirely and reduce their dose by at least 25% at 6-month follow-up than the control group. The secondary hypothesis is that Veterans receiving EMPOWER for Veterans will also experience fewer anxiety symptoms, better sleep quality, and overall health/quality of

life at 6-month follow-up. A supplemental analysis of benzodiazepine use only will be conducted at 12 months, using VA databases to evaluate whether changes identified persist over time.

Impact

Considering that electronically delivered interventions are inexpensive to disseminate once they have been developed, this project has an excellent chance to promote health care value by creating an easily scaled-up, method of reducing the prevalence of the widespread risk of long-term benzodiazepine use to improve Veterans' health.

2.0 Introduction

Long-term dependence on prescribed benzodiazepines is a public health challenge which has been the subject of significant concern in multiple countries, including Israel, the United Kingdom, and the United States (Bachhuber et al., 2016; Lembke et al., 2018) [1-2]. Although useful as short-term medications for some patients (e.g., those experiencing transitory sleep difficulties), benzodiazepines convey significant risk, particularly when taken long-term. The range of adverse outcomes includes cognitive decline, falls, motor vehicle accidents, benzodiazepine dependence, and opioid-benzodiazepine overdose (Park et al., 2020; Sun et al., 2017; VA Pharmacy Benefits Management Academic Detailing Service, 2021) [3-5]. Further, although in the short-term benzodiazepines can relieve their most common indications – anxiety and sleep disturbance – in the long-term they often exacerbate them (Lader, 2011) [6]. Therefore, effective strategies are needed to help people discontinue long-term benzodiazepine use.

Although therapist-delivered cognitive-behavioral psychological interventions (e.g., for insomnia and anxiety) can reduce benzodiazepine use (Gould et al., 2014) [7], limits on patient willingness and health care system resources make providing individual psychotherapy to even a plurality of long-term benzodiazepine users very challenging. A less costly, more scalable, approach to reducing benzodiazepine use is to use the Internet to directly provide patients with structured materials that impart risk information and encourage them to reduce or cease consumption, either on their own or in consultation with their prescribing physician. As such interventions that do not require patients to travel and that can be accessed at any time and from virtually any place could be attractive to individuals who might not access clinic-based psychotherapy.

Interventions that operate on smartphones and desktop computers are increasingly being studied as a low-cost, highly accessible method for changing substance use behavior (Garnett et al., 2017; Cheung et al., 2020) [8,9]. Although this intervention delivery method has not to our knowledge been evaluated with benzodiazepine cessation or reduction, it has shown success among hazardous drinkers. For example, Cunningham and colleagues (Cunningham, [name] et al, 2009; Cunningham, Neighbors, Wild & [name], 2012) [10,11] have demonstrated that heavy drinkers reduce alcohol consumption in response to short, self-administered assessments of alcohol consumption coupled with personalized feedback on risks and on variance from normative population consumption. Further, electronically delivered interventions are inexpensive to disseminate and increasingly preferred by patients (Erbes et al., 2014; Klee et al., 2016) [12,13], increasing their likelihood of broad adoption in healthcare systems (Damschroder & Hagedorn, 2011) [14].

A promising model for such an intervention comes from a Canadian clinical trial of self-management materials that provided information about the risks of long-term benzodiazepine use and suggested strategies for tapering down. The Eliminating Medications Through Patient Ownership of End Results (EMPOWER) study demonstrated that older long-term benzodiazepine users who were mailed paper and pencil materials were over five times more likely to discontinue use of benzodiazepines than were controls (Tannenbaum et al., 2014) [15]. If EMPOWER works in electronic form, it would greatly expand its potential reach.

One national health care system in which such an intervention could be particularly valuable is the US Veterans Health Administration (VHA). The VHA is a government-financed health care system which offers comprehensive care to over nine million individuals with prior service in the U.S. military. In the VHA, 355,298 Veterans were prescribed benzodiazepines in the fiscal year 2016, almost two-thirds (63.6%) of whom took them for three months or more (VA Pharmacy Benefits Management, 2017) [16]. The VHA population includes many elderly individuals and many who take prescribed opioids, further increasing the risk of long-term benzodiazepine use.

To tailor EMPOWER to the veteran population, our research team worked with VHA patients, physicians, and administrators; we then worked with software developers to convert the intervention to a computer-delivered format we call EMPOWER for Veterans (Electronic Version). This protocol describes how EMPOWER for Veterans will be tested in a randomized clinical trial evaluating whether it is effective with a markedly different population and format than in the initial Canadian study. The primary hypotheses of the RCT are that long-term users of benzodiazepines who are assigned to receive EMPOWER for Veterans will be significantly more likely than controls to cease taking benzodiazepines or reduce their benzodiazepine dose by at least 25% at six-month follow-up. The secondary hypotheses are that relative to controls, participants receiving EMPOWER for Veterans will improve more on anxiety symptoms, sleep quality, and overall health/quality of life at six-month follow-up. As functional outcomes were not measured in the original EMPOWER study, this is a unique contribution of the present trial. In addition to being important in themselves, these three secondary outcomes may moderate or mediate participants' response to EMPOWER for Veterans. For example, if secondary outcomes improve upon benzodiazepine tapering, participants may be more likely to continue to full cessation. In contrast, if functional outcomes deteriorate, patients and their physicians may be inclined to abandon EMPOWER for Veterans; if this were a common result it would likely reduce the adoption of EMPOWER for Veterans within VHA. Also, part of our secondary analysis will be to explore whether any effects of EMPOWER for Veterans observed on our primary outcomes at six-month follow-up are maintained at 12-month follow-up.

3.0 Objectives

The overall goal of this project is to create an electronic version of EMPOWER tailored to Veterans receiving VHA primary care. Specifically, this study maintains three aims. This protocol is specific to Aim 2, which is described in detail as the following:

Aim 2: Conduct a randomized clinical trial to test the effectiveness of the tailored, electronic intervention (EMPOWER for Veterans) on VA primary care patients' benzodiazepine cessation/reduction and functional outcomes at follow-up.

The primary hypotheses of Aim 2 are that in a clinical trial of 170 Veterans who are long-term users of benzodiazepines, those receiving the EMPOWER for Veterans intervention will be significantly more likely at 6-month follow-up to (a) cease taking benzodiazepines entirely, and (b) reduce their benzodiazepine dose by 25% or more. A secondary hypothesis of Aim 2 is that, relative to controls, Veterans receiving EMPOWER for Veterans will improve more on three functional outcomes: anxiety, sleep quality, and overall health/quality of life.

This protocol only describes Aim 2 research activities, which will occur at the Central Arkansas Veterans Health Care System; and as a result, IRB approval is being requested to conduct Aim 2 only.

We plan to request approval for Aim 3 at the Palo Alto Veterans Healthcare System, since the work for that aim will be conducted at that site.

5.0 Study Procedures

Refer to section 5.1-5.7 for a detail of study procedures.

5.1 Study Design

Study Design and Setting

This study will be a randomized controlled trial (N=170) conducted at the Central Arkansas Veterans Healthcare System (CAVHS) and the Minneapolis VA Health Care System to include their affiliated sites. Patients with at least one primary care appointment in the last year will be screened for eligibility.

Participants

We will generate a list of potentially eligible participants using VHA's centralized patient database (CDW) for both CAVHS and Minneapolis VA Health Care System.

Inclusion criteria include 1) having a designated primary care provider at CAVHS, Minneapolis VA and their affiliated sites, 2) taking prescribed benzodiazepines for three months or longer (as measured in the Electronic Health Record [EHR]), 3) taking their medication in tablet (as opposed to capsule) form, 4) internet access and a desktop computer, tablet, or smartphone.

Exclusion criteria include 1) palliative care patient, 2) current diagnosis of dementia, schizophrenia, seizure disorder and/or spinal cord injury, and 3) visual impairment (such that they are unable to read on a webpage.) Study staff will contact and screen potential participants for other exclusion criteria that cannot be determined through the centralized patient database (i.e., internet access, lack of access to a smartphone or tablet, visual impairment).

Although there is an indicator in the CDW to determine if medication is in tablet or capsule form; study staff will assess medication form during the screening process to ensure we do not inadvertently include someone taking capsule. Additionally, there is an indicator in the CDW to assess visual impairment via diagnostic codes (e.g., H53 visual disturbance, H54 blindness and low vision); however, study staff will assess via self-report during the screening process. These inclusion criteria are based on both the original EMPOWER study and feedback from stakeholders (Veterans, VA operational partners) in Aim 1 and from the CAVHS IRB review committee.

To be eligible, participants will be taking any benzodiazepine medications. Based on feedback from our operational partners, their data indicates that ~99% of Veterans are taking clonazepam, lorazepam, alprazolam, diazepam, or temazepam. Therefore, we expect that most, if not all, Veterans enrolled will be taking one of these medications. Data collected from the CDW, medication type and dose, will be coded as a crosswalk and maintained in an unidentifiable (with only study ID's) database. All inclusion and exclusion criteria will be coded as a cross walk and maintained an unidentifiable (with only study ID's) database.

Recruitment

Individuals meeting study eligibility criteria will be mailed an opt-out letter with information about the study, an invitation to participate, an option to 'opt-out' of study participation and study staff contact information. The recruitment mailing will also include a copy of the study informed

consent and HIPAA authorization forms, and a pre-addressed postage-paid envelope. Study staff will contact the individual 10-14 days after mailing the invitation letter unless the potential participants return the opt-out card. We will make up to 6 phone calls to attempt to contact the potential participant. If we do not reach them after 6 calls, they will be placed on our “do not contact” list. If a Veteran chooses to contact study team via SMS (text message), study staff will respond to the text message with request to schedule time to talk with the Veteran via VA cell phone. Study staff will inform the Veteran that SMS messaging is not encrypted and suggest that the Veteran delete sent and received text messages after receiving.

Prior to conducting informed consent, the study team will ask screening questions to confirm initial eligibility and confirm with the Veteran that they have a paper copy of the informed consent and HIPAA authorization forms in hand and agree to preferred method of obtaining ICF and HIPAA documents prior to initiation of the informed consent process.

The study team may re-share the ICF and HIPAA authorization via mail, fax, or via VA Outlook email using Azure Rights management Services (RMS) when the Veteran has the ability to print out hard copies to use in the informed consent process.

Study staff will send an unencrypted email with instructions from the User Guide for External Azure RMS Recipients first to confirm the Veteran’s email address and help recipient to open the email message. Study team will then send a second email with the informed consent and HIPAA authorization documents attached, which will include instructions on how to securely transmit pictures or scanned images using RMS.

Once the potential participant has available hard copy or DocuSign informed consent and HIPAA authorization documents, the study staff will review the study purposes, procedures, risk, and benefits and allow time for questions. Study staff will inform Veterans that if they are assigned to the EMPOWER condition, they may voluntarily choose to taper their benzodiazepines; however, this is not required to participate in the study. This is also stated on the EMPOWER website.

Participate Compensation:

Veterans will be compensated for their time, checks for \$30 will be mailed to them 4-6 weeks after completing the baseline and 6-month assessments. Participants who complete both the baseline and 6-month assessments will receive a total of \$60.

Sample Size

The original EMPOWER study reported a more than five-fold difference in benzodiazepine cessation and reduction rates with an OR greater than 8, which converts to a Cohen’s d greater than 0.8 Tannenbaum et al., 2014) [15]. However, we powered the present study using a more conservative estimate of the intervention effect based on a recent meta-analysis of 17 clinical trials (Boumparis et al., 2017) [17] showing that computer-delivered interventions demonstrate an effect size on drug use only somewhat lower than medium (0.36).

To attain 80% power with .05 type I error rate to detect a medium effect size of 0.35 with intra-class coefficient of .008 (based on the original EMPOWER study; Tannenbaum et al., 2014) [15] for the primary outcomes of benzodiazepine cessation/reduction, 66 patients per group will be needed. Assuming an 80% six-month follow-up rate, this will require enrollment at baseline of

170 participants (i.e., 85 per group). All data will be analyzed by the study biostatistician ([name]).

Randomization

Participants randomized to the EMPOWER condition will be provided information about how to dispose of any unwanted benzodiazepines should they choose to reduce or discontinue their medication. Specifically, we will share with the participant that they may contact their primary care doctor to obtain a Medication Disposal Patient Kit and/or identify nearby locations (via the website artakeback.org) for the Arkansas medication takeback program.

To produce the taper schedule, participants will enter their current benzodiazepine dosage into the EMPOWER website. A tapering schedule will then be generated based on the self-reported number of tablets that the patient is taking each time they take their medication. The tapering schedule will last up to 21 weeks with each day's target pill consumption graphically displayed on a calendar (e.g., full-pill, half-pill, quarter pill, or no pill).

The EMPOWER for Veterans website will also include practical tips for managing the taper process including when to contact one's primary care physician, along with CAVHS and Minneapolis VA pharmacy contact information. Study Participants will be notified of need to obtain a pill cutter along with instructions to contact pharmacy to obtain pill cutter if they do not already have one. The study team will not be providing pill cutters to study participants. We learned from the previous Aim 1 focus groups with Veterans, that most Veterans know how to

obtain a pill cutter on their own since they are easily and cheaply obtainable online or through pharmacies.

Control condition

Participants assigned to the control condition will be asked to continue to follow any provider recommendations regarding benzodiazepine use (i.e., treatment-as-usual). Control participants will also be informed that access to the EMPOWER for Veterans materials will be made available to them at the end of the study (i.e., at 12-months post randomization).

Data Collection

Participants in both conditions will be asked to complete a baseline and 6-month assessment. We also plan to collect data from the CDW on participants' benzodiazepine use at baseline, six-month and 12-month follow-up.

Risks:

The risks associated with study participation include the possibility that a few of the questions (e.g., those inquiring about anxiety symptoms) may cause some psychological discomfort; however, based on our experience in prior VA studies, we expect this to be minimal. It is also possible that Veterans may experience some discomfort with tapering their benzodiazepines. The EMPOWER tool for Veterans will encourage participants to discuss any concerns they might have with discontinuing/reducing their medication with their providers.

To mitigate risks associated with medication tapering a CPRS flag and/or CWAD posting will be created depending on the site.

CAVHS: Study staff will enter a flag in CPRS for Veterans enrolled to indicate study participation along with information that study participants randomized to the EMPOWER intervention arm may choose to self-taper benzodiazepines while enrolled in this study. The flag will also include a link to the EMPOWER site.

Minneapolis VA: Study staff will, in lieu of a flag, will create a post in the Clinical Warning/Advance Directive (CWAD) Posting. This will serve as a mechanism of notifying healthcare providers that the Veteran is participating in the EMPOWER study.

Benefits:

For Veterans assigned to EMPOWER for Veterans, benefits may include help with discontinuing/reducing their benzodiazepines use and/or giving them information about alternative strategies to help with sleep/anxiety (common indications for prescribing benzodiazepines). Also, Veterans often find it gratifying to participate in efforts that can help other Veterans in need. To that affect, it is believed that this research will help other Veterans reduce or cease the use of benzodiazepines and improve some functional outcomes, like anxiety, sleep quality, and overall health/quality of life.

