5.3 Informed Consent Procedures

The informed consent process will be conducted over the telephone by IRB approved research staff who have experience consenting Veterans for intervention studies within VHA. Following the informed consent discussion using the IRB approved informed consent document, Veterans interested in participating in the study will be asked to complete and sign informed consent document and HIPAA authorization forms via the approved methods described below, according to their preference and access to email, printing, and scanning. For CAVHS Veterans

enrolled in the study, the informed consent and HIPAA authorization documents will be scanned into CPRS. A research flag and enrollment note will be entered into CPRS. This note will include identification of the IRB approved mechanism used to obtain documentation of informed consent.

Study staff will obtain documentation of informed consent and HIPAA authorization from individuals who are interested in participating in one of 3 ways: Return-by-Mail, Return-by-Digital Image Capture, Return-by-DocuSign

For Minneapolis study participants, CAVHS research staff will access the study participant's Minneapolis CPRS medical record and create a CWAD posting to include the CAVHS IRB required research flag information. Additionally, study staff will enter a progress note to include templated information required in CAVHS participants' enrollment note adding the study participant's primary care provider (PCP) as an additional signer. This will serve as a mechanism to specifically notify the PCP that the Veteran is participating in the study.

5.3.1 Return by DocuSign. DocuSign is a VA cloud Software as a Service (SaaS) solution approved for use in VA research for the purpose of sending digital documents to patients and collection of their signatures. After completing screening questions, the study team contact will send a DocuSign envelope (email containing links to the study documents) to interested potential participants. The email will contain a reminder for the recipient to not sign the documents prior to the scheduled contact time to review the documents and have questions answered.

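### The take-back locator given to every EMPOWER participant is for the Arkansas program only, so Minneapolis participants have no usable one; section 5.3 should also say whether the CAVHS note carries the PCP as signer.

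*Combined protocol and SAP*

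**What the plan says.** The Methodology part of the abstract describes a "two-arm individually randomized controlled trial with 170 Veterans at the Central Arkansas Veterans Healthcare system and the Minneapolis VA Health Care System", together with affiliated sites.

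**Disposal.** Section 5.1, Experimental condition, states: "Participants randomized to the EMPOWER condition will be provided information about how to dispose of any unwanted benzodiazepines". Two routes follow, joined so that a participant may use either or both. First, "they may contact their primary care doctor to obtain a Medication Disposal Patient Kit". Second, they may "identify nearby locations (via the website artakeback.org) for the Arkansas medication takeback program". A little later, the same part describes tips on the website for managing the taper, "along with CAVHS and Minneapolis VA pharmacy contact information".

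**Notice to providers.** Section 5.1, Risks, states: "To mitigate risks associated with medication tapering a CPRS flag and/or CWAD posting will be created depending on the site". It then specifies a chart flag at CAVHS, which says that intervention-arm participants may self-taper and links to the EMPOWER site. At Minneapolis a CWAD posting replaces the flag. Section 5.3 says of CAVHS: "A research flag and enrollment note will be entered into CPRS". For Minneapolis it describes the posting plus a progress note built on the CAVHS enrollment-note template, with the PCP as additional signer, and explains: "This will serve as a mechanism to specifically notify the PCP that the Veteran is participating in the study".

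**The concern.** The disposal information is written for the whole intervention arm, but its only locator belongs to one of the two states. A Minneapolis participant who reduces or stops, has tablets to discard and follows the study's own instruction is sent to a program in Arkansas. What is at stake is a practical safety aid for a controlled medicine, in a trial whose tool invites people to taper at home over as long as 21 weeks.

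The provider-notice text raises a lesser question of consistency. The step by which the PCP is told directly is spelled out for Minneapolis, while the CAVHS paragraph does not mention it. A reader cannot tell whether the sites differ or whether the CAVHS text is just shorter.

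**Working it through.** The plan gives no figure on this point and none is needed. The check sets the provisions side by side by site, using sections 5.1, 5.3 and 6.0.

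| Provision | CAVHS | Minneapolis | Where |
|---|---|---|---|
| Disposal kit through primary care doctor | yes | yes | 5.1 Experimental condition |
| Take-back locator | Arkansas program | none named | 5.1 Experimental condition |
| Pharmacy contact details | yes | yes | 5.1 Experimental condition |
| Chart-level notice | flag | CWAD posting | 5.1 Risks; 5.3 |
| PCP as additional signer on the note | not stated | yes | 5.3 |
| Adverse-event procedure | yes | yes | 6.0 |

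**Locator.**
1. The instruction covers all participants randomized to EMPOWER and is not limited to CAVHS.
2. The one website is described as serving the Arkansas program.
3. The trial also enrols at Minneapolis and affiliated sites.
4. From 1 to 3, Minneapolis participants in the EMPOWER arm have no locator that serves them. The kit remains.
5. The pharmacy contacts name both sites, and section 6.0 says its procedure covers both. The authors therefore wrote for two sites elsewhere. Section 3.0 still places the Aim 2 activities at CAVHS, so text left from a single-site plan is a plausible explanation, though this is inference.

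**Signer.** The Minneapolis sentence in section 5.3 can be read in two ways. The signer may be part of the CAVHS template being reused, or it may be a Minneapolis addition. The CAVHS paragraph gives the consent mechanism as content of its note and is silent on signers. The text supports only that the step is not stated for CAVHS.

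**Size.** With 85 planned per arm and a share *p* enrolled at Minneapolis, about 85 × *p* participants would be given the Arkansas-only locator. The documents do not give *p*. Purely as an assumed range, *p* = 0.30 gives 85 × 0.30 = 25.5 and *p* = 0.70 gives 85 × 0.70 = 59.5. These count people offered the information, not people left without a way to dispose of tablets.

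**The case against.** The strongest reply is that little is lost. The kit is listed first and is open at both sites, and the locator is an optional extra. Tapering is voluntary, so many participants may never have tablets to discard. The participant materials were not available and may already have been adapted for Minneapolis. All of this stands, and it limits the importance of the point. It does not change the fact that the protocol instruction, as written, gives one site a locator for another state.

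Three stronger readings are tempting, and the documents support none of them.

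- *CAVHS PCPs are not told.* This infers too much from silence. The signer may belong to the CAVHS template. The mitigation that section 5.1 names for taper risk is the flag or posting, which exists at both sites, and the CAVHS flag mentions self-tapering explicitly. How far a flag reaches a PCP unprompted is not described. Section 6.0 also provides a study nurse, physician contact and follow-up within 24 hours, at both sites.
- *The site difference biases the primary outcome.* Prescribing does define the primary outcomes, and section 5.6 names no site term. But randomization is individual, and the notices follow enrolment in both arms. A difference between sites in provider notice would fall on both arms, and no bias between arms is shown.
- *A known number of participants is affected.* Any count depends on a site split that the plan does not state, and it would include people who never taper.

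**Conclusion.** The locator point holds: every EMPOWER participant is directed to the Arkansas program, and no counterpart is named for Minneapolis. It is a small site-consistency gap in participant information, softened by the kit route that both sites share. It has no claimed effect on power, the estimand or the comparison between arms.

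The signer point is a request for clarification only. It is not a finding that a safeguard is absent at CAVHS.

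The conclusion rests on the protocol's own description of the website as the route to the Arkansas program; the website was not consulted. It also assumes that no site-specific disposal text exists in the participant materials or in sections 1.0 and 4.0, none of which could be checked.

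**What to change.** 1. In the disposal information in section 5.1, Experimental condition, and in the matching participant material, add a take-back locator that serves Minneapolis and its affiliated sites. The cost is about one line of text and the usual approval of a revised document.
2. As a minor clarification, reconcile section 5.1 (Risks) with section 5.3 by stating whether the CAVHS enrollment note also carries the PCP as additional signer. If it already does, one sentence settles the matter. If it does not, the protocol should say that the sites differ. Extending the step to CAVHS would not be free: it would alert the PCPs of more control participants, in a trial where prescribing is the outcome, and could make procedures differ between earlier and later enrollees. That decision belongs to the investigators, and nothing here requires it.
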